14.11.1 Dose modifications for patients from protocol SOM230B2219

For patients who do not tolerate the protocol-specified dosing schedule, dose adjustments are permitted in order to allow the patient to continue the study treatment. The following guidelines need to be applied:

Cushing's disease: At any time during the study the pasireotide dose may be reduced by 300 μ g b.i.d for safety or tolerability reasons. Dose may be increased to 600 or 900 μ g b.i.d if tolerability issues have resolved per investigator's discretion.

Acromegaly: Dose up-titration of pasireotide LAR to 60 mg i.m. once/28 days will be allowed in patients without adequate levels of GH and IGF-1 (no reduction of mean GH level to <2.5 μ g/L and no normalization of IGF-1 to within normal limits (age and sex related)) as determined locally. A dose reduction by 20 mg will be permitted in case of tolerability issues, but the patient may return to previous dose once tolerability issues are resolved.

Dose should also be modified for adverse events as described in [Table 14-13](#).

Any dose change must be recorded on the respective Dosage Administration Record CRF.

14.11.2 Dose modifications for patients from protocol SOM230B2305

For patients who are unable to tolerate the protocol-specified dose level, dose adjustments are permitted in order to keep the patient on study drug. (Refer to [Table 14-13](#)). At any time during the study, patients with an early morning (between 8 and 10am) serum cortisol < 3 μ g/dl and a UFC measurement < LLN or symptoms suggestive of hypoadrenalinism (e.g. postural hypotension, nausea, and abdominal pain) and a UFC measurement <LLN should have their dose reduced.

During the roll-over, the investigator may reduce the dose in 300 μ g s.c. b.i.d. steps at any time if the patient does not tolerate the given pasireotide dose. The minimum dose to be administered will be 300 μ g s.c. b.i.d.. If the patient does not tolerate the 300 μ g s.c. b.i.d. dose, he/she will be withdrawn from the study.

These changes must be recorded on the Dosage Administration Record.

Table 14-13 Dose modification for AEs, excluding LFT increase, QT prolongation and hyperglycemia

Adverse event	Action
CTCAE grade \leq 2	No drug adjustments
CTCAE grade \geq 3 and assessed as study drug related	Reduce pasireotide to the next dose level. If the AE improves to grade \leq 2 before the next administration, increase dose back to the prior dose. If the dose is increased and the AE recurs at a grade \geq 3, the dose should be reduced again. The patient should stay on this lower dose and no further dose titrations are allowed. If the AE does not improve to grade \leq 2, the dose is to be reduced further. If the AE does not improve to grade \leq 2 on the minimum study dose, the treatment should be stopped. The patient should be discontinued and followed up for safety.

For the management of LFT increase, QT prolongation, and hyperglycemia refer to specific instructions provided in [Appendix 2](#), [Appendix 3](#) and [Appendix 4](#).

14.12 Appendix 12: Dose modification information for patients with Cushing's receiving pasireotide s.c in combination with cabergoline (SOM230B2411)

Table 14-14 Dose and treatment schedule

Study treatments	Pharmaceutical form and route of administration	Dose	Frequency and/or Regimen
Pasireotide	Subcutaneous	0.3mg, 0.6mg, and 0.9mg	Twice a day
Cabergoline	Oral	0.5mg or 1.0mg	Once a day

Pasireotide untreated patients: will begin their treatment with pasireotide 0.6mg twice a day monotherapy for 8 weeks. If biochemical control is not achieved by the end of the 8-week period, and the 0.6mg dose is well tolerated, the dose of pasireotide will be increased to 0.9mg twice a day for another 8 weeks. If biochemical control is still not achieved at 0.9mg twice a day and the dose is well tolerated, the combination treatment of pasireotide 0.9mg twice a day plus cabergoline 0.5mg once a day will be given for another 8 weeks. If biochemical control is not yet achieved either during or at the end of the 8-week period, cabergoline dose will be increased to 1.0mg once a day.

If a patient shows high sensitivity to pasireotide 0.6mg bid resulting in cortisol values <LLN and/or signs/symptoms consistent with the diagnosis of hypocortisolism, the dose of pasireotide can be decreased to 0.3mg bid. Despite the dose reduction, some patients may still present with cortisol values <LLN and/or signs/symptoms consistent with hypocortisolism; in this case the dose of pasireotide can be further reduced to 0.3 mg qd in order to achieve and maintain normal cortisol levels.

If the 0.9mg twice a day dose is not tolerated and biochemical control is not achieved, patient will begin combination treatment of pasireotide at 0.6mg twice a day plus cabergoline at 0.5mg once a day for 8 weeks. If during or at the end of the 8-week period, the biochemical control is not achieved, the combination dose will be increased to pasireotide at 0.6mg twice a day plus cabergoline at 1.0mg once a day for 8 weeks. The patient will continue with the highest combination dose of 0.6mg pasireotide twice a day plus 1.0mg cabergoline once a day, or 0.9mg pasireotide twice a day plus 1.0mg of cabergoline once a day for 8 weeks. (see [Table 14-15](#))

If patient does not tolerate 0.6mg twice a day, the dose of pasireotide should be decreased to 0.3mg twice a day. If pasireotide 0.3mg twice a day does not lead to biochemical control after at least 8 weeks of treatment, combination with cabergoline as described above can be initiated (see [Table 14-15](#)).

If patient cannot increase from 0.6mg twice a day to 0.9mg twice a day due to safety, and is not yet biochemically controlled, combination with cabergoline 0.5mg qd can be initiated right away with pasireotide at 0.6mg twice a day (see [Table 14-15](#)).

If patient is being escalated to 0.9mg twice a day, but cannot tolerate the dose, dose should be reduced to 0.6mg twice a day. If the latter dose does not lead to biochemical control, combination with cabergoline as described above can be initiated (see [Table 14-15](#)).

If combination pasireotide and cabergoline 0.5mg once a day is not tolerated, the dose of cabergoline can be reduced to 0.5mg every other day. If 0.5mg every other day is not tolerated, and biochemical control is not achieved, patient should be considered for discontinuation if no clinical benefit is derived (see [Table 14-15](#)).

If combination pasireotide and cabergoline 1.0mg once a day is not tolerated, the dose of cabergoline can be reduced to 1.0mg every other day. If 1.0mg every other day is not tolerated, and biochemical control is not achieved, patient should be considered for discontinuation if no clinical benefit is derived (see [Table 14-15](#)).

The minimum treatment of any regimen is 8 weeks. Patients losing biochemical control at any time point after the 8 week period will have the dose of the study medication increased immediately to the next level provided that the dose is well tolerated.

Table 14-15 Pasireotide and cabergoline dose modification steps for pasireotide un-treated patients

Pasireotide: pasi Cabergoline: cabe	Starting dose level	Dose modification level – 1	Dose modification level – 2	Dose modification level - 3	Dose medication level - 4
Modification # 1	0.6mg bid pasi ^a	0.3mg bid pasi ^b	0.3mg bid pasi + 0.5mg cabe qd ^b	0.3mg bid pasi + 1.0mg cabe qd	
Modification # 2	0.6mg bid pasi ^b	0.9mg bid pasi ^b	0.9mg bid pasi + 0.5mg qd cabe ^b	0.9mg bid pasi + 1.0mg qd cabe	
Modification # 3	0.6mg bid pasi ^b	0.9mg bid pasi ^a	0.6mg bid pasi ^b	0.6mg bid pasi + 0.5mg cabe qd ^b	0.6mg bid pasi + 1.0mg cabe qd
Modification # 4	0.6mg bid pasi ^c	0.6mg bid pasi + 0.5mg qd cabe ^b	0.6mg bid pasi + 1.0mg cabe qd		
Modification # 5	0.9mg bid pasi ^{ab}	0.6mg bid pasi + 0.5mg qd cabe ^b	0.6mg bid pasi + 1.0mg qd cabe		
Modification # 6	0.3, 0.6 or 0.9mg bid pasi + 0.5mg qd cabe ^a	0.3, 0.6 or 0.9mg bid pasi + 0.5mg every other day cabe ^{ab}	Discontinuation if no clinical benefit		
Modification # 7	0.3, 0.6 or 0.9mg bid pasi + 1.0mg qd cabe ^a	0.3, 0.6 or 0.9mg bid pasi + 1.0mg every other day cabe ^{ab}	Discontinuation if no clinical benefit		

^aDose modification is initiated if the current dose is not tolerated

^bDose modification is initiated if biochemical control is not achieved

^cDose cannot be increased to the next level due to toxicity but biochemical control is not achieved

Patients currently treated with maximal tolerated doses of pasireotide monotherapy:
0.3mg bid, 0.6mg bid or 0.9mg bid, for at least 8 weeks but did not achieve biochemical control will begin their combination treatment of pasireotide at 0.3mg, 0.6mg or 0.9mg bid plus 0.5mg of cabergoline once a day at study entry. They will continue the treatment for 8 weeks. If

biochemical control is not achieved at the end of the 8-week period, the dose of cabergoline will be increased to 1.0mg once a day and continue with the combination treatment for the remainder of study treatment.

If combination pasireotide and cabergoline 0.5mg once a day is not tolerated, the dose of cabergoline can be reduced to 0.5mg every other day. If 0.5mg every other day is not tolerated, and biochemical control is not achieved, patient should be considered for discontinuation if no clinical benefit is derived (see [Table 14-16](#)).

If combination pasireotide and cabergoline 1.0mg once a day is not tolerated, the dose of cabergoline can be reduced to 1.0mg every other day. If 1.0mg every other day is not tolerated, and biochemical control is not achieved, patient should be considered for discontinuation if no clinical benefit is derived (see [Table 14-16](#)).

The minimum treatment of any regimen is 8 weeks. Patients losing biochemical control at any time point after the 8-week treatment period at the starting combination dose will have the dose of the study medication increased immediately to the next level provided that the dose is well tolerated (see [Table 14-16](#)).

Table 14-16 Pasireotide and cabergoline dose modification steps for patients currently treated with maximal tolerated doses of pasireotide monotherapy

Pasireotide: pasi Cabergoline: cabe	Starting dose level	Dose modification level – 1	Dose modification level – 2
Modification # 1	0.3, 0.6 or 0.9mg bid pasi + 0.5mg qd cabe ^a	0.3, 0.6 or 0.9mg bid pasi + 0.5mg every other day cabe ^a	Discontinuation if no clinical benefit
Modification # 2	0.3, 0.6 or 0.9mg bid pasi + 0.5mg qd cabe ^b	0.3, 0.6 or 0.9mg bid pasi + 1.0mg qd cabe ^a	
Modification # 3	0.3, 0.6 or 0.9mg bid pasi + 1.0mg qd cabe ^a	0.3, 0.6 or 0.9 mg bid pasi + 1.0mg every other day cabe ^a	0.3, 0.6 or 0.9mg bid pasi + 0.5mg qd cabe

^aDose modification is initiated if the current dose is not tolerated

^bDose modification is initiated if biochemical control is not achieved

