Patients will receive the same dose of pasireotide LAR as the last dose in the parent study. The maximum dose to be administered is 40 mg. Dose can be increased from 10 to 30 mg and from 30 to 40 mg. During the roll-over study, the timing of the dose adjustments will be based on mUFC values, at the investigators discretion but must include a duration of at least 3 months on a current dose prior to up-titration and no tolerability issues are present. Patients receiving the 40 mg dose after Month 12 without tolerability issues that require a dose reduction will remain at this dose regardless of mUFC status ($\leq 1x$ ULN or $> 1 x$ ULN).

Dose down-titration

Patients with tolerability issues can have their dose decreased as deemed necessary by the investigator (see [Table 14-5](#)). The dose can be increased again after the tolerability issue resolves. Patients unable to tolerate a minimum dose of 5 mg will be discontinued.

These changes must be recorded on the Dosage Administration Record CRF.

Table 14-5 Dose modification for AEs, excluding LFT increase, QT prolongation and hyperglycemia

Adverse event	Action
AE CTC grade ≤ 2	No drug adjustments
AE CTC grade ≥ 3 and assessed as study drug related	Reduce pasireotide LAR i.m. dose from: 40mg to 30 mg 30 mg to 10 mg 10 mg to 5mg 5mg - discontinue If AE improves to grade ≤ 2 before the next administration, increase dose to that prior to the dose reduction unless investigator opinion is to remain on current dose. If the dose is increased and the AE recurs at CTC grade ≥ 3 , the dose should be reduced again and the patient should stay on this lower dose and no further dose titrations are allowed. During the first 7 months of treatment, only 1 blinded dose decrease is allowed. If the AE persists at grade ≥ 3 after reduction, the patient is to be discontinued. After the first 7 months, If AE does not improve to grade ≤ 2 the dose is to be reduced further until the 5 mg dose is reached. If the AE does not improve to grade ≤ 2 on the minimum dose (5 mg) the patient will be withdrawn.

For the management of LFT increase, QT prolongation, and hyperglycemia refer to specific instructions provided in [Appendix 2](#), [Appendix 3](#) and [Appendix 4](#).

14.7 Appendix 7: Dose modification information for dumping syndrome patients receiving pasireotide s.c or LAR (from protocol SOM230X2203)

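### For SOM230B2305 patients, section 14.11.2 calls for dose reduction on low cortisol at any grade, while its own Table 14-13 orders no change at grade 2 or below and its minimum dose can leave no step down

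*Protocol*

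**What the plan says.** Section 14.11.2 of the protocol (within Appendix 11) gives dose guidance for patients from SOM230B2305, who receive pasireotide s.c. for Cushing's disease. Four of its statements matter here.

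- **Low-cortisol sentence.** It applies at any time to "patients with an early morning (between 8 and 10am) serum cortisol < 3" µg/dl with UFC below the lower limit of normal, and to patients with hypoadrenal symptoms "and a UFC measurement <LLN should have their dose reduced". No CTCAE grade is mentioned. The example symptoms are postural hypotension, nausea and abdominal pain.
- **Table 14-13.** Its title is "Table 14-13 Dose modification for AEs, excluding LFT increase, QT prolongation and hyperglycemia". For grade 2 or below the action is "No drug adjustments". For grade 3 or above and drug-related, the dose goes down a level, then back to the prior dose if the event improves to grade 2 or below before the next administration.
- **Minimum dose.** "The minimum dose to be administered will be 300" µg s.c. b.i.d.; a patient who does not tolerate that dose is withdrawn.
- **Tolerability reductions.** The investigator may step down by 300 µg b.i.d. at any time if the dose is not tolerated.

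The opening of Appendix 11 lists the s.c. levels as 300, 600 and 900 µg b.i.d. Section 6.2 leaves dose changes to the investigator's judgment and refers sites to the appendices, without saying which instruction prevails when two differ.

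**The concern.** The sentence and the table sit in one section, address the same patients and can be triggered by the same finding. For a mild or moderate event they give opposite instructions about continued exposure, at the same dose, to a drug that lowers cortisol. At the lowest dose the sentence asks for something the section does not allow.

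The main stake is patient safety and uniform conduct across sites. The stake for the analysis is smaller. Hypocortisolism is an adverse-event-of-special-interest group in SAP 8.2. SAP 7.4.1 tabulates adverse events requiring dose adjustment or interruption, and SAP 7.3 tabulates reasons for dose change. Which line a site follows feeds directly into the last two. It affects event counts only at the margin: under protocol 8.1.1 and 8.1.2.1 a laboratory abnormality is an adverse event if it is symptomatic, clinically significant, needs therapy, or leads to a change in study medication. Only an asymptomatic value that is otherwise not significant and not treated would depend on the dose action for its status.

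**Working it through.** No figure in the documents bears on this. Sections 10.7 and 10.8 are not applicable and no hypothesis is tested, so the check sets the instructions side by side.

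**Step 1. Does the trigger fall inside Table 14-13?** Yes, on three grounds.

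- The title excludes only liver-test increases, QT prolongation and hyperglycemia.
- Under 8.1.1 a laboratory abnormality that requires a change in study medication is an adverse event, and the low-cortisol sentence calls for such a change.
- The symptoms that the sentence lists are adverse events in their own right.

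**Step 2. What does each instruction say for a B2305 patient who meets the trigger?**

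| Current dose | Event grade | Low-cortisol sentence | Table 14-13 | Result |
|---|---|---|---|---|
| 600 or 900 µg b.i.d. | 2 or below | Reduce | No adjustment | Contradiction |
| 600 or 900 µg b.i.d. | 3 or above, drug-related | Reduce | Reduce; back to prior dose once grade 2 or below | Agree at first, then conflict if the trigger is still met |
| 600 or 900 µg b.i.d. | 3 or above, not drug-related | Reduce | Silent | No conflict |
| 300 µg b.i.d. | 2 or below | Reduce | No adjustment | Contradiction, and no lower step is permitted |
| 300 µg b.i.d. | 3 or above, drug-related | Reduce | Reduce; stop if no improvement at the minimum dose | No lower step; the table gives an end point if the event persists |
| 300 µg b.i.d. | 3 or above, not drug-related | Reduce | Silent | No lower step; outcome unspecified |

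**Step 3. Re-escalation.** The return to the prior dose depends on grade alone. A patient whose event has improved to grade 2 but whose UFC is still below normal, with low morning cortisol or symptoms, is sent up by the table. The same patient still meets a sentence that applies at any time and sends the dose down.

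**Step 4. The floor.** Section 6.1.1 bars doses not indicated in the parent study, and 14.11.2 fixes the minimum at 300 µg b.i.d. The minimum-dose sentence ties withdrawal to intolerance. The specific discontinuation criteria in 7.1.5.1 are hepatic, QT-related and hyperglycemia-related; none concerns cortisol. The section therefore does not say what follows when the cortisol trigger is met at the floor.

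**The case against.** The best answer is that a specific instruction governs a general one. The low-cortisol sentence is specific, the table is a default, and the same section already lets the investigator reduce for intolerance without a grade limit. That is a reasonable reading and many sites would adopt it. But it is not written down. Where specific guidance displaces the table, the protocol names the topic in the table's title and points to Appendices 2 to 4. Hypocortisolism is not named.

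It can also be said that 7.1.5.1 allows withdrawal on physician decision or where staying would be harmful, so a patient at 300 µg b.i.d. is not trapped. That is correct: the minimum-dose text is a gap, not an instruction to stay on the dose.

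A reader might infer a wider contradiction across all Cushing's patients. The documents do not support it.

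- Appendix 6 says that certain patients "will remain at this dose regardless of mUFC status", but it covers SOM230G2304 patients on LAR. The sentence is limited to 40 mg after Month 12 without tolerability issues that require a reduction. No patient is subject to both it and 14.11.2.
- SOM230B2219 Cushing's patients have no cortisol sentence, but 14.11.1 permits reduction at any time for safety or tolerability.
- Appendix 12 gives SOM230B2411 patients a further step down for persistent low cortisol. Dosing follows each parent study by design, so this difference is not in itself an error.

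**Conclusion.** The point holds for SOM230B2305 patients only. For an event of grade 2 or below, the low-cortisol sentence and Table 14-13 contradict each other with no stated precedence. For a drug-related event of grade 3 or above at 600 or 900 µg b.i.d., they agree at first and can conflict on re-escalation. At 300 µg b.i.d. the reduction cannot be carried out at any grade, and the section gives no outcome specific to the cortisol trigger.

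The trigger is narrower than below-normal cortisol alone: it needs UFC below normal plus either serum cortisol under 3 µg/dl or symptoms. The grade 2 or below contradiction assumes that some triggering events are grade 1 or 2. If every one were grade 3 or above, the re-escalation and minimum-dose problems would remain. The documents do not say how many B2305 patients rolled over or how often the trigger is met, so the number affected cannot be estimated. The effect on the safety tables is limited and descriptive. The reason to correct the text is that it bears on patient safety and can be repaired by wording.

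**What to change.** In 14.11.2, reconcile three pieces of text and state which governs: the low-cortisol sentence, Table 14-13 (both the grade 2 or below row and the return to the prior dose), and the minimum-dose sentence. The text should leave one answer for each row of the comparison above, including the patient who meets the trigger at 300 µg b.i.d. If the specific sentence is meant to prevail, the table's title or a footnote can say so; if the table is meant to prevail, the sentence can say so. Table 14-13 also serves SOM230B2219 patients through 14.11.1, so the wording should make clear which patients it reaches. The choice of clinical rule belongs to the sponsor.

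The cost is appendix wording, made through a protocol amendment with the approvals that section 12.1 requires. The wording change does not itself require new data fields or SAP analyses. Whether sites routinely measure morning cortisol and UFC in these patients is not documented: section 7.2.2 refers monitoring to the label or the Investigator Brochure and leaves local laboratory tests to investigator judgment and standard of care.

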1 LIST OF ABBREVIATIONS

AE	Adverse event
AESI	Adverse Event of Special Interest
CSR	Clinical Study report
СТС	Common Toxicity Criteria
CTCAE	Common Terminology Criteria for Adverse Events
DI	Dose Intensity
FAS	Full Analysis Set
EC	Ethic Committee
eCRF	Electronic Case Report Form
EOT	End Of Treatment
IIT	Investigator Initiated Trial
IRB	Institutional Review Board
LAR	Long Active Release
MedDRA	Medical Dictionary for Drug Regulatory Affairs
PASS	Post Authorization Safety Study
PT	Preferred Term
SAE	Serious Adverse Event
SAP	Statistical Analysis Plan
s.c.	Sub-cutaneous
SOC	System Organ Class

2 INTRODUCTION

This statistical analysis plan (SAP) describes all planned analyses for the clinical study report (CSR) of study CSOM230B2412, an open-label, multi-center, Phase IV, roll-over study in patients who have completed a prior Novartis-sponsored pasireotide (SOM230) study and are judged by the investigator to benefit from continued treatment with pasireotide.

The content of this SAP is based on protocol CSOM230B2412 Amendment 5.0. All decisions regarding final analysis, as defined in the SAP document, will be made prior to database lock.

2.1 CLINICAL OBJECTIVES

The purpose of the study is to evaluate the long-term safety.

2.2 STATISTICAL DESIGN / MODEL

This is a multi-center, open label, phase IV, roll-over study of pasireotide in patients being treated in previous Novartis Oncology-sponsored studies and who are benefiting from treatment with pasireotide by their parent study investigator. The parent studies that are eligible to participate in the roll-over study were decided by Novartis. Investigator initiated trials (IIT) will not be included.

There will be no screening period for this study. At the enrollment visit, the patient will be consented to the study and eligible patients can start their treatment with pasireotide. Patients must return to the clinic at any given time as per standard of care, however only four study visits per year (with the exception of 5 visits within the first year) will be recorded for patients receiving pasireotide s.c. and monthly visits for those patients receiving pasireotide LAR.

All adverse events and serious adverse events will be collected continuously throughout the study.

At every visit, the investigator is required to confirm that the patient continues to have clinical benefit and may continue receiving study treatment. Study design is described in Figure 2-1 below.

Figure 2-1 Study Design

*Note: The starting dose of pasireotide should be the same dose as that which the patient was receiving in the parent study at roll over.

